#### Hypotheses and Specific Aims:

This Stage II randomized, controlled, longitudinal trial seeks to assess the acceptability, feasibility, and effects of a driving decision aid use among geriatric patients and providers. This multi-site trial will (1) test the driving decision aid (DDA) in improving decision making and quality (knowledge, decision conflict, values concordance and behavior intent); and (2) determine its effects on specific subpopulations of older drivers (stratified for cognitive function, decisional capacity, and attitudinally readiness for a mobility transition). Our overarching hypotheses are that the DDA will help older adults make high-quality decisions, which will mitigate the negative psychosocial impacts of driving reduction, and that optimal DDA use will target certain populations and settings.

The challenge of how to support older adults making decisions about driving gains urgency with the aging population, the increase in older adults with cognitive impairment, and the fact that widespread use of driverless cars is likely distant. Although informational websites and self-assessment tools exist, a key knowledge gap remains: how to help older drivers actually make decisions about their driving in a way that is individualized and supports autonomy. In clinical medicine, decision aids are used to increase patient knowledge and decision quality. A web-accessible driving decision aid (DDA) was iteratively developed (NIH Model Stage I) to meet all international decision aid standards and is now ready for efficacy testing (Stage II), but questions remain. How do cognitive or emotional factors influence a decision aid's utility or timing for use? Should it be given to all older drivers at a certain age, or with certain conditions? Should there be pre-screening for a driver's cognitive state or readiness to consider changes? When and where should the DDA be used?

In this 5-year research project, our goals are to test how much the DDA improves outcomes in older drivers and to identify who benefits most from the DDA. We seek to facilitate optimal decision-making by identifying and leveraging cognitive, emotional and motivational factors.

Aim 1: In a multi-site, two-armed randomized trial of older drivers (n=300;  $\geq$ 70 years) and family members, to test the effect of a web-based DDA as compared to control (web-based information only on:

1a. Immediate decision quality (measured by the Decisional Conflict Scale), hypothesizing that more DDA participants will make high-quality decisions;

1b. Longitudinal psychosocial outcomes at 12 and 24 months, hypothesizing that DDA participants will have reduced prevalence of depressive symptoms and of decision regret but maintained life space

1c. Longitudinal driving behaviors (including reduction or cessation) at 12 and 24 months, hypothesizing that the DDA- although not intended to direct participants to continue or stop driving- will lead to changes.

Aim 2: Using data from Aim 1, to use stratified analyses to determine the DDA's effects in specific subpopulations, including:

2a. Older drivers with versus without cognitive impairment, hypothesizing that the DDA will improve decision quality more in cognitively intact drivers;

2b. Older drivers with maintained versus impaired decisional capacity, hypothesizing that the DDA will improve decision quality more in drivers with maintained decisional capacity;

2c. Older drivers who are attitudinally more ready versus less ready for a mobility transition, hypothesizing that the DDA will improve decision quality more in drivers who are ready for transition.

Aim 3: Through qualitative interviews and surveys with key stakeholders (older drivers, family members, healthcare providers, and experts in the field), to identify the desirable settings for DDA use, including:

3a. acceptability and suggestions for modifications or targeted use with subpopulations;

3b. preferred locations, such as clinical settings, community programs, or at home.

The proposed study will provide the groundwork for tailoring intervention delivery and preparing for its implementation.

## **Background and Significance:**

"Driving retirement" is a critical life decision. As of 2015, there were over 25 million drivers aged  $\geq$ 70 years, and 70% of adults aged  $\geq$ 85 years still had a driver's license. Driving is closely linked to well-being, and driving retirement can negatively impact independence and mental health. A recognized national goal, therefore, is to help older drivers stay on the road as long as it is safe, as maintaining mobility and community involvement promotes health and longevity. Safety remains a consideration since some older drivers are at increased risk of crashes and fatal crash rates increase after age 75, but generally older drivers pose a greater risk to themselves than to the community around them. Precise estimation of an individual driver's risk remains difficult, as on-road testing is costly and not always available and office-based assessment is often impractical and not routine. Thus, decisions about driving retirement typically involve some combination of the older driver, involved family members or trusted friends, and healthcare providers, depending on the individual's circumstances and preferences.

Decision-making is a multi-dimensional process. Decisions are affected by complex interactions between myriad internal and external factors, including cognitive ability, decisional capacity, emotions, personality, and environmental or pragmatic factors. Older drivers fear losing their

COMIRB No: 19-0059

independence, being abandoned, or becoming a burden on others, while simultaneously fearing causing harm to others on the road, and decisions about driving are complicated by financial and lifestyle considerations, such as alternative transportation options. The mechanisms of decision-making also change over an individual's life, and the process can be further complicated by attitudinal factors (e.g., emotional readiness for a major transition) and cognitive function. Understanding how key attitudinal and cognitive factors affect decisions about driving gains critical urgency with the aging population in the US who rely heavily on driving themselves.

Cognitive impairment complicates driving decisions. While physical conditions and medications can affect driving, Alzheimer's disease and other forms of progressive cognitive impairment have the strongest link to both driving risk and the need for eventual driving cessation. Lack of insight, education, and/or recognition of cognitive impairment by spouses and families are all likely contributing factors. Given the estimate of almost 16 million older adults in the US with dementia by 2050, the decision-making needs around driving for this group—and the transportation needs for our society—will be significant. This does not even factor in the large number of older adults with other acute or chronic medical conditions that also negatively impact cognition and driving, such as stroke, Parkinson's Disease, and visual impairment. The role of family members, trusted friends, and healthcare providers in supporting a driver through driving retirement gains additional importance in the context of cognitive impairment or concerns about decisional capacity.

Decision aids- based on evidence and theory- can help with difficult decisions. Decision aids are tools that facilitate decision-making and have been developed and used for medical issues from acne treatment to weight control, but rarely (to date) for decisions about "life issues." A unifying, recommended model for decision aid development is the Ottawa Decision Support Framework (Figure 1). which draws upon concepts from psychology, decision conflict, social support, and self-efficacy. The framework posits that decisional needs (e.g., knowledge, conflict/uncertainty, and values) affect decision quality, with the highest quality decision being one that is both informed and reflective of the individual's values. Decision guality, in turn, affects patient actions and, ultimately, impacts both health outcomes and patient's feelings about the decision. The overall assertion is that the highest quality decision will have the best outcome for the patient. Therefore, decision aids can enhance decision quality by addressing unmet decisional needs; specifically, decision aids facilitate complicated decisions by (a) identifying the decision to be made. (b) describing risks and benefits of various options, (c) assisting the patient in clarifying personal values, and (d) activating the patient for decision-making. In a Cochrane review of 115 randomized trials (with 34,444 participants total), decision aids improved multiple decision outcomes, including knowledge, satisfaction, decisional conflict and regret, and communication.

Older drivers need a tool to help their decision-making. Various guides and self-assessment tools exist to help older drivers and their families think about driving, but what was missing was a tool to walk a driver through the process of deciding whether or not to stop driving. Decision aids have been developed for financial, long-term care, and end-of-life issues, and a small pilot (n=12) found a paper-based driving decision aid (DDA) acceptable and useful, although their tool is specific to individuals with dementia in Australia (which has different laws and systems of alternative transportation). Healthwise, a nonprofit organization that provides decision support tools and other services to enhance patient-centered decision making,

Table 1. Driving Decision Aid content						
Section	Description					
Get the Facts	Clarifies decision (whether to stop or continue driving, watching for warning signs) and presents basic facts about driving safety and aging.					
Compare options	Explains what is involved in each option, including benefits and risks or side effects and stories from others.					
Your Feelings	Helps individual rate, on scales, their feelings about reasons to stop or continue driving (concern about crashes, comfort with driving, concern from others, alternative transportation).					
Your Decision	Encourages individual to rate, on a scale, if they are leaning towards stopping or continuing driving. This section also includes a quiz and printable summary.					

released a DDA in 2015 for US drivers with or without dementia (Table 1). The tool was developed according to international decision aid standards, is available online, and is easily accessible by 25% of clinicians in the United States. Unclear, however, is its effect on decision quality (i.e., satisfaction) or longer-term psychosocial outcomes, or which groups might benefit most from it (Figure 1).

Attitudinal readiness for driving retirement also affects decisions. The Transtheoretical Model has been applied to the stages of transition involved with driving cessation, with the

# AUTO Study Protocol: Version Date: 12/22/21

PI: [name], MPH

COMIRB No: 19-0059

idea that drivers progress—albeit at different rates—from pre-contemplation (the older driver with no concerns or plans to stop) through maintenance (the former driver who has found usable alternative transportation; Figure 2). The Transtheoretical Model posits ambivalence is a natural consequence of considering changes to health behavior, with each stage representing definable activities along the continuum of readiness for change. The Assessment of Readiness for Mobility Transition (ARMT) is a validated, attitudinal measure developed to help providers identify an older adult's openness to changes and loss of transportation-related mobility. Drivers with higher ARMT total scores are less prepared for and more resistant to discussing or using transportation alternatives because they believe mobility loss inevitably leads to loss of independence and becoming a burden to others. In contrast, drivers with lower ARMT total scores are more likely to openly and directly discuss mobility loss without the perceived risk to their self-identity. Ideally, the ARMT could guide ongoing, personalized mobility planning, as healthcare providers could tailor discussions by identifying an individual's stage along the spectrum.

Older drivers want time to prepare for changes- but discussions and decisions are often postponed. The Trans-theoretical Model posits (Figure 2), and prior work confirms, that older drivers want time to prepare for driving retirement. In a qualitative meta-synthesis of existing studies, our team found: driving discussions are emotionally charged; context matters; providers are trusted and viewed as authority figures; communication should occur over a period of time rather than suddenly; and older adults desire agency in the decision to stop driving. Unfortunately, in the real-world these difficult conversations are often delayed until a crash occurs or a new medical or social crisis develops, leaving little time for preparation Engagement with healthcare providers is recommended for decisions about planning for future driving retirement, but this has been difficult to operationalize in routine clinical practice because of system constraints, leaving discussions in primary care to when significant safety concerns are already present and demand action. In a review of electronic health records (EHR) from 240 patients' primary care encounters over a one-year period, we found documented conversations occurred with only 8-15% of older patients in general internal medicine clinics and 28% of those in a geriatric clinic. Understanding the barriers and facilitators to decision aid use in clinical practice will be key for future research and real-world use. Given the estimated 17-year time lag from original research to implementation of evidencebased interventions into practice. it is critical to consider dissemination & implementation (D&I) frameworks when developing, testing and refining interventions.

Clinical and epidemiological research with older adults: The team has significant relevant experience in trials and longitudinal studies with older adults, though none of their current projects overlap with this trial. Drs. [name], [name], and [name] currently collaborate as Site PIs on the LongROAD study, an observational study of a cohort of 2990 healthy older drivers in five states that is currently in year 3 of longitudinal follow-up. For the LongROAD study, they recruited 1200 drivers in Denver and San Diego in only 21 months. Through her NIA Beeson K23 project, [name] recruited 315 older drivers (65% participation) for an on-road test and one-month follow-up, with 90% overall retention. [name] also has experience recruiting and following older adults and their family members, including as PI of a large trial (426 dyads; NIH/NIA R01) testing a decision aid for caregivers of women with ADRD. Our study team also has experience in examining the emotional aspects of driving and mobility changes, including prior collaborations using the ARMT and qualitative studies of the views of older drivers and healthcare providers.

Research with cognitively-impaired older adults: [name] has extensive experience conducting quantitative and qualitative research with cognitively impaired older adults and their family members. The focus of her work is on medical decision making for older adults with ADRD and early identification of ADRD in primary care. In her role as co-leader of the Outreach and Recruitment Core for the NIA funded Indiana Alzheimer Disease Center, she supports IU faculty who want to conduct research with persons with ADRD and their family members. [name] is a board-certified clinical neuropsychologist who has published extensively on cognitive aging, MCI and ADRD as well as cognitive impairment in the context of decision making in old age. He is the former recipient of an NIA Beeson K23 award on decision making in old age and current PI of an R01 (NIH/NIA) focused on the racial differences in decision making in old age.

Qualitative methods: [name] has extensive experience in qualitative methods, including interviews and focus groups with older adults and healthcare providers. [name] and [name] have also conducted significant qualitative work exploring decisional needs and cognitive biases surrounding implantable defibrillators, left ventricular assist devices, and advance care planning/hospice.

## **Outcome Measures and Analysis:**

AUTO Study Protocol: Version Date: 12/22/21 PI: [name], MPH COMIRB No: 19-0059 Key measures in this trial (Table 3, additional details below) are tied directly to our theoretical framework (Figure 1) and assess DDA effects (Aim 1) and potentially differential subgroup effects (Aim 2).

Immediate outcomes: Our primary outcome will be the DDA's effect on decision quality, a fundamental element of the Ottawa Decision Support Framework as a precursor to behavior change (Figure 1). A high quality decision is defined as an informed patient making a decision consistent with their values.

-Decision Conflict: The Decisional Conflict Scale (DCS) measures internal conflict or ambivalence about the decision, with higher internal conflict (or ambivalence) indicating the decision is less in-line with personal values. The DCS is closely linked to overall decision quality and is a recommended primary outcome measure. The DCS estimates decisional conflict through personal perceptions of issues such as uncertainty in choosing options, modifiable factors contributing to uncertainty, and effective decision-making (e.g., expressing satisfaction with the choice). The DCS is a 16-item scale (with Likert scale response options) that has high reliability and test-retest correlation (Cronbach's alpha coefficients > 0.78). In prior work, the DCS has been shown to discriminate between known groups who make or delay decisions (effect size 0.4-0.8), with lower scores indicating low decision conflict (and greater likelihood of implementing a decision). Scores <25 (out of 100 total) are associated with implementing decisions.

-Values Concordance: We will use the "Values Clarity" subscale of the DCS to examine specifically how much participants feel their decisions are in line with their values. Three DCS items are summed and multiplied by 8.33; scores range from 0 (extremely clear) to 100 (extremely unclear about personal values).

-Knowledge: Questions will assess concepts about driving presented in the DDA and control group website.

-Self-Efficacy: We will measure decision self-efficacy (one's self-confidence or belief in one's ability to make decisions) using the Decision Self-Efficacy Scale, as decision aids can increase self-efficacy. Transformed scores range from 0 (extremely low) to 100 (extremely high self-efficacy).

Longitudinal outcomes: Key longitudinal outcomes, linked to our theoretical framework (Figure 1), are psychosocial and mobility-related.

-Depression: We will measure depression using the PROMIS 4-item scale, with higher scores indicating higher depression. All PROMIS scores are analyzed as standardized T-scores (mean=50, SD=10).

-Decision regret: The Ottawa Decision Regret Scale. This validated measure correlates with decision satisfaction and conflict, and overall quality of life. Scored from 0-100, high scores represent higher regret.

-Life space: Life space is a global measure of mobility and community engagement. The Life-Space Assessment instrument (UAB Study of Aging) is a validated tool assessing recent mobility and function. Composite scores range from 0 (bedbound) to 120 (travel out of town

AUTO Study Protocol: Version Date: 12/22/21 PI: [name], MPH COMIRB No: 19-0059 every day without assistance); scores of  $\leq$ 60 are correlated with lower levels of social participation and higher mortality.

-Driving behaviors: We will assess driving frequency (days per week), avoidance in certain situations (e.g., night), driving cessation (none, partial, complete), and self-reported crashes (≥1 versus none).

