## AUTO Study Protocol: Version Date: 12/22/21 PI: [name], MPH COMIRB No: 19-0059 **Table 3. Key study measures**. Shown in relation to measurement point (pre- or post- DDA or website

Participant, and analytic plan. • = about self,  $\circ$  = as surrogate about older driver

		[name]/friends			Analytic Plan				
Domaiı	n and Key Measures	En	roll	F/u	Enr	oll	F/u			
		Pref	Post		Pre	Post			Hypoth.	Scoring
Immediate outcome										
Decision Conflict	Decisional Conflict Scale (DCS)	•	•	•	٠	•	•	1° Outcome	1a, 2a, 2b, 2c	Score <25
Knowledge	Knowledge questionnaire	•	•	•		•	•	2° Outcome	1a	Descriptive (cat.)
Values concordance	DCS Values Clarity subscale	٠	٠	•	٠	٠	٠	2° Outcome	1a	Descriptive (cat.)
Self-efficacy	Decision Self-Efficacy scale	•	•	•		•	•	2° Outcome	1a	Descriptive (contin.)
Longitudinal outcome										
Depression	PROMIS depression	٠		٠				2°	1b	T-score >50
								Covariate	1c	Descriptive (contin.)
Decision regret	Ottawa Decision Regret Scale			•			•	2° Outcome	1b	Descriptive (contin.)
Life space	Life-Space Assessment	٠		•			0	2° Outcome	1b	Descriptive (contin.)
Driving behaviors	Amount; reduction or cessation	•		•			0	2° Outcome	1c	Descriptive (cat.)
Subgroups										
Cognitive	5 minute MoCA			٠			•	Eligibility		Score ≥21
screening								Covariate	•	
Cognitive function	BTACT, OTMT	•						Stratify	2a	Normal vs. impaired
Insight	Beck Cognitive Insight Scale	٠		٠				Stratify	2a	R-C index ≥3
Decisional capacity	SPACED	•		•				Stratify	2b	# correct answers
Attitudes about	ARMT	٠		٠				Stratify	2c	Mean score ≥3.57
anning								Covariate	1c	_0.07

	Drivers	Family/fri	Analytic Plan				
Domaii	n and Key Measures	Enroll F	/u Enroll	F/u			
		PrePost	Pre Post			Hypoth.	Scoring
Other covariates							
Demographics	E.g., age, gender, race/ethnicity, marital/home status, education, income, urban/rural	•	• •	•	Covariate	all	Descriptive (cat.)
Physical health	Medical history, Activities of Daily Living, PROMIS global health	•	•	•	Covariate	all	Descriptive (cat.)
Mental health	PROMIS Emotional Support, Social Isolation; Perceived Stress Scale	•	•		Covariate	1b, 1c	Descriptive (cat.)
Personality	TIPI	•			Covariate	1c, 2c	Descriptive. (cat.)
Driving behaviors	Crashes, self-driving technologies	•	•	0	Covariate	1c	Descriptive (cat.)
Driving resources	Alternative transportation, support	•	••	• 0	Covariate	1c	Descriptive (cat.)
Driving education	Use of websites, courses, or other material driving or cessation	•	• •	•	Covariate	1c	Descriptive (cat.)

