**Randomization**: At each site, enrolled drivers (with their family members) will be randomly assigned in equal numbers to the DDA or control arm (Figure 4). To reduce bias and aim for balance among arms, we will randomize patients in blocks with randomly varied block sizes of 4 and 6. While RAs delivering the intervention to patients cannot be blinded to treatment, we will conceal allocation using a centralized, computer-generated list that RAs will access only after enrollment. Other study staff, including a different RA (whenever possible) doing follow-up calls, will be blinded to study arm.

**Baseline Measurements & Intervention**: The driver and family member will be randomized to the same arm but will complete all study measures and interventions separately from each other. For each participant (including those enrolled in person as well as those enrolled remotely by phone), the RA will use a study tablet or laptop to administer the introductory questionnaire (Figure 4, Table 3). In the intervention arm, participants will then complete the web-based DDA; control group participants will be directed to the NIA "Older Drivers" website. After completing the DDA or website review, all participants in both arms will answer questions about their knowledge, values, and plans related to driving cessation (Table 3). For family members, questions will generally be about the older driver, though there will be specific questions concerning their relationship, frequency of contact, and possible co-dependence for transportation. Whenever possible, participants will receive a printed handout of either their DDA results or the NIA webpage (for those enrolled in person) or will receive instruction from the RA about how to save an electronic copy of the DDA results or the NIA webpage (for those enrolled in person) or the NIA webpage (for those enrolled remotely by phone).

**Identifying driving risk**: At the request of the DSMB, the study team will use American Academy of Neurology (AAN) guidelines to identify drivers who are at moderate risk for being unsafe to drive (https://www.aan.com/PressRoom/home/GetDigitalAsset/8471). Per AAN

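### The values concordance outcome is scored only with the DCS Values Clarity subscale, whose stated anchors describe clarity about values and do not vary with the choice made

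*Combined protocol and SAP*

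**What the plan says.** Hypotheses and Specific Aims lists the elements of decision making and quality that the decision aid (DDA) is to improve: "knowledge, decision conflict, values concordance and behavior intent". Outcome Measures and Analysis, under Immediate outcomes, gives the governing definition: "A high quality decision is defined as an informed patient making a decision consistent with their values". That is a relation between what a person decides and what the person values.

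The Values Concordance entry in the same section says the Values Clarity subscale of the DCS will be used "to examine specifically how much participants feel their decisions are in line with their values". The next sentence gives the scoring: "Three DCS items are summed and multiplied by 8.33; scores range from 0 (extremely clear) to 100 (extremely unclear about personal values".

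In Table 3 the only measure against values concordance is the "DCS Values Clarity subscale". It is marked as a secondary outcome for hypothesis 1a, with scoring given as descriptive and categorical. The analysis text for Aim 1a mentions values concordance once, among components of decision quality to be examined in additional analyses.

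**The concern.** Two adjacent sentences describe different things. The purpose sentence is about the fit between a decision and the person's values. The scoring sentence is about certainty over the values themselves, and no decision appears in it. A label that promises fit, attached to a score anchored on certainty, will be read as evidence of fit.

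This matters because the two arms differ in a way that could plausibly affect clarity directly. Table 1 shows that the DDA asks users to rate their own reasons for stopping or continuing. Potential Challenges and Strategies says the control website does not lead the person through the decision. Felt clarity could therefore rise in the DDA arm without choices becoming more consistent with values, and the plan would file that gain under concordance. Since the protocol defines decision quality partly by consistency with values, a mislabelled secondary result would bear on how the main finding is explained.

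**Working it through.** **1. Reproduce the stated range.** Inputs from Outcome Measures and Analysis: three items, multiplier 8.33, range 0 to 100.

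Score = 8.33 × (sum of three items).

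100 / 8.33 = 12.0, or 4.0 per item, which implies coding from 0 to 4. The documents say only that the items are Likert-type, so this coding is an inference.

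| Item coding | Lowest score | Highest score |
|---|---|---|
| 0 to 4 | 0 | 99.96 |
| 1 to 5 | 24.99 | 124.95 |
| 0 to 3 | 0 | 74.97 |
| 0 to 5 | 0 | 124.95 |
| 1 to 4 | 24.99 | 99.96 |

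Of these, only 0 to 4 gives the stated range. The arithmetic of the subscale is sound.

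**2. Does the score depend on the choice?** Apply the stated anchors to four drivers.

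| All three items at | Choice fits values | Choice conflicts with values |
|---|---|---|
| clear end (0 each) | 8.33 × 0 = 0 | 8.33 × 0 = 0 |
| unclear end (4 each) | 8.33 × 12 = 99.96 | 8.33 × 12 = 99.96 |

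The rows differ and the columns do not. By its anchors the score separates clear from unclear people and carries no information on whether the choice fits.

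**3. Does anything else in the plan supply the comparison?**

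- Study Design and Research Method (Baseline Measurements & Intervention) says "all participants in both arms will answer questions about their knowledge, values, and plans related to driving cessation". The sentence refers to Table 3. The only values measure there is this same subscale, and no measure of plan or intention is listed.
- The DDA's own ratings of reasons, and of leaning towards stopping or continuing (Table 1), are intervention content. They are not a listed trial measure and would exist in one arm only.
- Reported driving behaviour is listed in Table 3, but no analysis sets it against values.
- The analysis text for Aim 1a contains no pairing of values with choice.

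**4. Overlap with the primary outcome.** The DCS has 16 items, so the subscale supplies 3 / 16 = 18.75% of them. If all 16 are coded 0 to 4 and equally weighted (an assumption), the three items can contribute up to 12 × 100 / 64 = 18.75 points to the 0-100 total. Some agreement between this secondary outcome and the primary one is built in.

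**5. Type of variable.** The scoring rule yields a 0-100 score. Table 3 calls it categorical, and no cut-point is given for it.

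**The case against.** The strongest reply is that the protocol aims at perceived alignment, how participants feel about their decision, and not at an external match between values and behaviour. It also treats the total DCS as an indirect sign of alignment, reading higher conflict as a decision less consistent with values. The wording of the three subscale items and of the other 13 is not in the documents, so none can be shown to be silent on perceived fit. This stands. A reader might infer that the trial can say nothing at all about concordance; the documents do not support that.

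A reader might also infer that the score runs backwards, rewarding discordant drivers and penalising concordant ones. It does not. The table above shows a score that ignores the choice: a clear driver whose choice fits also scores 0.

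It is also fair to say that the subscale is openly named, that its membership of the DCS is disclosed, and that reporting a subscale beside its total is ordinary practice. The overlap is therefore something to state alongside the result and is not itself an error.

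The perceived-alignment reply does not reconcile the purpose sentence with the anchors that follow it. Feeling that a decision fits one's values and being clear about those values are different, and the stated anchors describe only the second.

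**Conclusion.** The point holds in limited form. As planned, the values concordance outcome measures clarity about values, and no listed measure or analysis compares values with the choice in both arms. A clarity gain would be reported under one of the four decision-quality effects named in the aims. The conclusion rests on the stated anchors, since item wording is not available, and on the questionnaire containing no more than Table 3 lists.

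The effect is on the interpretation of one secondary outcome. Hypothesis 1a rests on the proportion with DCS below 25, so the primary endpoint, alpha, power and sample size are unaffected.

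A reader might want to attach a probability that the trial would declare a spurious concordance benefit. The documents do not support one: they give no expected effect on this subscale, and the plan lists the outcome as descriptive without specifying a formal test.

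**What to change.** In Outcome Measures and Analysis and in Table 3:

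- rename the outcome values clarity, and make the purpose sentence agree with the anchors;
- analyse it as a continuous 0-100 score, in place of a categorical outcome with no cut-point;
- state that its three items are part of the 16-item primary DCS.

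In Hypotheses and Specific Aims, limit the claim so that no conclusion about concordance is drawn from this subscale.

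Then check the post-exposure questionnaire. If it already collects values ratings and a stop-or-continue plan in both arms, a separate concordance variable can be prespecified, with a written rule for when plan and ratings agree. If it does not, no such variable should be promised, because Table 3 does not show the data for it.

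The wording changes need no new visits or data. The cost is that the trial gives up the concordance label for this result.
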